9.6 Ophthalmic assessments

Ophthalmic assessments are done for patients who enter the long-term follow-up study from blinded studies with comparator treatments arms or patients who have been off fingolimod for 90 days or greater. Assessments are completed as needed.

The incidence of macular edema events during the long-term follow-up study part I will be summarized for the safety set. The number and percentage of patients with any macular edema events and particular event type (macular edema presence in left or right eye) will be provided based on either dilated assessment or OCT assessment (by ophthalmologist) if available. The number and percentage of patients with history of diabetes mellitus and the number and percentage of patients with history of diabetes mellitus and macular edema assessment done will also be provided to support data summary.

The patients with macular edema events during the long-term follow-up study part I will also be listed for the safety set. All records will be listed for a particular patient if there is at least one macular edema event. A separate listing for visual acuity assessment during the long-term follow-up study part I will be provided as support.

9.7 Pulmonary function tests

Pulmonary function tests are only done as needed during the study to monitor safety. It includes parameters: forced expiration volume in 1 second (FEV₁), forced vital capacity (FVC), diffusion capacity for carbon monoxide (D_LCO), and the derived FEV₁/FVC ratio. Observed values, percentage of predicted values for these four parameters, respiratory infection status, and smoking status during the long-term follow-up study part I will be listed for the safety set.

9.8 Skin assessment

Skin assessment is only done as needed during this study to monitor safety. Patients with skin abnormalities (any dermatologic findings suspicious for being precancerous or cancerous, or if a skin disorder, for example abnormal cancerous lesion, is diagnosed) during the long-term follow-up study part I will be listed for the safety set.

10 Sample size and power considerations

Given that this is a long-term follow-up study with primary descriptive purpose, no formal sample size calculation will be used to determine enrollment in this study. The sample size is defined by the number of patients coming from ongoing/new core/extension trials that meet the inclusion and exclusion criteria. It is estimated that about 5000 patients will be enrolled in this trial.

Appendices

Appendix A: Clinically notable laboratory values

Only selected lab parameters identified as notable which have been shown to be sensitive to fingolimod exposure are included.

CRITERIA FOR NOTABLE LABORATORY ABNORMALITIES

Notable Values		
Laboratory Variable	Standard Units	SI Units
LIVER FUNCTION AND RELATED VARIABLES		
SGOT (AST)	>82 U/L	>82 U/L
SGPT (ALT)	>90 U/L	>90 U/L
Total bilirubin	≥ 2.0 mg/dL	≥ 34.2 μmol/L
Alkaline Phosphatase	>280 U/L	>280 U/L
RENAL FUNCTION / METABOLIC AND ELECTROLYTE VARIABLES		
Glucose`	≥200 mg/dL	≥11.11 mmol/L
Creatinine	≥2.0 mg/dL	≥176 umol/L
Amylase	≥ 300 U/L	≥ 300 U/L
Cholesterol	≥ 240 mg/dL	≥ 6.21 mmol/L
Triglycerides	≥300 mg/dL	≥3.39 mmol/L
BUN	≤ 2 mg/dL ≥ 30 mg/dL	≤ 0.7 mmol/L ≥ 10.7 mmol/L
Sodium	< 125 mEq/L >154 mEq/L	< 125 mmol/L >154 mmol/L
Chloride	≤85 mEq/L ≥119 mEq/L	≤ 85 mmol/L ≥119 mmol/L
Potassium	≤ 3.0 mEq/L ≥ 6.0 mEq/L	≤ 3.0 mmol/L ≥ 6.0 mmol/L
Magnesium	≤ 1.0 mg/dL ≥ 3.0 mg/dL	≤ 0.40 mmol/L (in all other countries) ≤ 0.41 mmol/L (in Canada)
Calcium	≤ 7.5 mg/dL ≥ 11.6 mg/dL	≤ 1.87 mmol/L ≥ 2.89 mmol/L
Phosphate	≤ 2.0 mg/dL ≥ 5.3 mg/dL	≤ 0.65 mmol/L ≥ 1.71 mmol/L

Notable Values		
HEMATOLOGY VARIABLES		
Hemoglobin	≤10.0 g/dL	≤100 g/L
Platelets (Thrombocytes)	≤100 k/mm ³ ≥600 k/mm ³	≤100 x 10 ⁹ /L ≥600 x 10 ⁹ /L
Leukocytes (WBCs)	≤2.0 k/mm ³ ≥15 k/mm ³	≤2.0 x 10 ⁹ /L ≥15 x 10 ⁹ /L
HEMATOLOGY VARIABLES: DIFFERENTIAL		
Granulocytes (Poly, Neutrophils)	≤ 1,000 /mm ³ ≥12000/mm ³	≤ 1 x 10 ⁹ /L ≥ 12 x 10 ⁹ /L
Lymphocytes	<200/mm ³ ≥8000/mm ³	<0.2 x 10 ⁹ /L ≥8 x 10 ⁹ /L
Red blood cells	<3,300,000/mm ³ >6,800,000/mm ³	<3.3 x 10 ¹² /L >6.8 x 10 ¹² /L

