## 6.5.4 Laboratory evaluations

Screening laboratory tests and routine blood samples as described in [Table 6-1](#) will be collected and analyzed by the central lab during Study Part One. During Study Part Two, laboratory tests will be collected and analyzed by the study site (i.e., locally, not using a central lab).

For Study Part One, details regarding collection of samples, shipment of samples, reporting of results, lab normal ranges and alerting abnormal values will be supplied to the site before site initiation in a study laboratory manual. The results of the analysis will be made available to each site by the central lab at the earliest 48 hours after receipt of the samples by the central lab. Extreme values, specified in the "Criteria for clinically notable laboratory values and vital signs" are further specified in [Appendix 1](#), which will generate a "phone alert" to the investigator.

For Study Part Two, samples will be collected and reported in accordance with local laboratory policies. Lab results will not be recorded in the eCRF, but will remain as source documentation for ongoing safety assessment.

Investigators will be asked to comment on any abnormalities on the respective lab result page, including a notation of the clinical significance of each abnormal finding in the patient's source documents. The laboratory sheets will be filed with the patient source documents.

Abnormal laboratory values or test results should be recorded as adverse events only if they induce clinical signs or symptoms, are considered clinically significant or require therapy. Abnormal laboratory values alone should not be recorded on the adverse event eCRF; however, any diagnoses (or signs or symptoms, if a diagnosis is not possible) associated with the abnormal findings should be recorded on the adverse event eCRF.

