#### CRITERIA FOR NOTABLE LABORATORY ABNORMALITIES

Notable Values		
Laboratory Variable	Standard Units	SI Units
LIVER FUNCTION AND RELATED VARIABLES		
SGOT (AST)	>82 U/L	>82 U/L
SGPT (ALT)	>90 U/L	>90 U/L
Total bilirubin	≥ 2.0 mg/dL	≥ 34.2 μmol/L
Alkaline Phosphatase	>280 U/L	>280 U/L
RENAL FUNCTION / METABOLIC AND ELECTROLYTE VARIABLES		
Glucose`	≥200 mg/dL	≥11.11 mmol/L
Creatinine	≥2.0 mg/dL	≥176 umol/L
Amylase	≥ 300 U/L	≥ 300 U/L
Cholesterol	≥ 240 mg/dL	≥ 6.21 mmol/L
Triglycerides	≥300 mg/dL	≥3.39 mmol/L
BUN	≤ 2 mg/dL	≤ 0.7 mmol/L
	≥ 30 mg/dL	≥ 10.7 mmol/L
Sodium	< 125 mEq/L	< 125 mmol/L
	>154 mEq/L	>154 mmol/L
Chloride	≤85 mEq/L	≤ 85 mmol/L
	≥119 mEq/L	≥119 mmol/L
Potassium	≤ 3.0 mEq/L	≤ 3.0 mmol/L
	≥ 6.0 mEq/L	≥ 6.0 mmol/L
Magnesium	≤ 1.0 mg/dL	≤ 0.40 mmol/L (in all other countries)
	≥ 3.0 mg/dL	≤ 0.41 mmol/L (in Canada)
Calcium	≤ 7.5 mg/dL	≤ 1.87 mmol/L
	≥ 11.6 mg/dL	≥ 2.89 mmol/L
Phosphate	≤ 2.0 mg/dL	≤ 0.65 mmol/L
	≥ 5.3 mg/dL	≥ 1.71 mmol/L

Notable Values		
HEMATOLOGY VARIABLES		
Hemoglobin	≤10.0 g/dL	≤100 g/L
Platelets (Thrombocytes)	≤100 k/mm  ≥600 k/mm 	≤100 x 10  /L ≥600 x 10  /L
Leukocytes (WBCs)	≤2.0 k/mm  ≥15 k/mm 	≤2.0 x 10  /L ≥15 x 10  /L
HEMATOLOGY VARIABLES: DIFFERENTIAL		
Granulocytes (Poly, Neutrophils)	≤ 1,000 /mm  ≥12000/mm 	≤ 1 x 10  /L ≥ 12 x 10  /L
Lymphocytes	<200/mm  ≥8000/mm 	<0.2 x 10  /L ≥8 x 10  /L
Red blood cells	<3,300,000/mm  >6,800,000/mm 	<3.3 x 10  /L >6.8 x 10  /L

NOTABLE VITAL SIGNS	
Vital Sign Variable	Notable Criteria
Pulse (beats/min)	>120bpm or Increase of ≥15 bpm from baseline Or < 50bpm or Decrease of ≥15 bpm from baseline
Systolic BP (mmHg)	≥160 mm Hg or Increase of ≥20 mm Hg from baseline Or ≤ 90 mm Hg or Decrease of ≥ 20 mm Hg from baseline
Diastolic BP (mmHg)	≥ 100 mmHg or Increase of ≥ 15 mm Hg from baseline Or ≤ 50 mmHg or Decrease of ≥ 15 mm Hg from baseline
Temperature (°C)	>38.3°C/ 101°F
Body Weight (kg)	±7% from baseline weight

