9.2 Laboratory

Hematology and blood chemistry data will be summarized separately by presenting descriptive statistics for baseline, post-baseline, and change from baseline values by lab parameter and visit. Shift tables (baseline to post-baseline values) based on normal range categories (low, normal, high, high & low) will be summarized separately for hematology and blood chemistry by lab parameter and visit.

Summaries of incidence of notable lab abnormalities for hematology and blood chemistry, reported from first dose of fingolimod among all studies, will present the number and percentage of patients with lab assessments satisfying notable criteria by visit. An overall study visit will be generated to indicate any notable abnormalities from post-baseline visits (including follow-up visits). Criteria for clinically notable laboratory values are specified in Appendix A. Percentages are based on the number of patients with non-missing lab result. A similar summary for patients with elevated liver function test values (elevation of 1, 2, 3, 5, 8 and 10 times the upper limit of normal) will be provided.

All summaries will be based on the fingolimod safety set.

Patients in the fingolimod safety set with notable post-baseline laboratory abnormalities will be listed separately for hematology and blood chemistry. All lab parameters with clinically notable criteria will be listed for a particular patient and visit if at least one of the parameters shows an abnormality. These listings will also indicate whether the lab result was above or below the normal range.

Patients with positive pregnancy test results during the long-term follow-up study part I will be listed for the safety set.

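### Notable magnesium has a high limit in mg/dL but none in SI units, so high values would not count as notable if the SI column is applied as printed

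*SAP*

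**What the plan says.** SAP Part I, Appendix A, sets the criteria for notable laboratory values in two columns, standard units and SI units. For magnesium the standard-unit cell is "≤ 1.0 mg/dL ≥ 3.0 mg/dL". The SI cell is "≤ 0.40 mmol/L (in all other countries) ≤ 0.41 mmol/L (in Canada". Protocol Appendix 1 holds the same SI entries, "≤ 0.40 mmol/L (in all other countries" and "≤ 0.41 mmol/L (in Canada".

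Other electrolytes in the same SAP table have both directions in SI: calcium is "≤ 1.87 mmol/L ≥ 2.89 mmol/L" and phosphate is "≤ 0.65 mmol/L ≥ 1.71 mmol/L".

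The table is used in two places. SAP Part I, 9.2, states: "Criteria for clinically notable laboratory values are specified in Appendix A". That section counts patients meeting the notable criteria by visit and overall, and lists patients with notable values. Protocol 6.5.4 ties telephone alerts to investigators in Part One to the extreme values in Appendix 1. Magnesium is one of the chemistry parameters collected (Protocol 6.5.4.2).

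**The concern.** The two columns should express one rule in two unit systems. For magnesium they do not: the standard-unit column flags both low and high values, and the SI column flags only low ones. The country split seems to occupy the space where an upper limit would stand.

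Safety is the primary objective, and the notable-value outputs are where extreme chemistry results are meant to be seen. SAP 9.2 lists a visit only if at least one parameter is notable there. A visit whose only extreme result was high magnesium would therefore drop out of the listing as well as the count, if the SI column governs. The same gap could carry into the alert settings.

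There is also a smaller mismatch. The low limit differs by country in SI but not in mg/dL, and SAP 9.2 gives no rule for using a country-specific limit in a pooled summary.

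**Working it through.** **Inputs from the documents** (SAP Part I, Appendix A; same entries in Protocol Appendix 1): magnesium limits of 1.0 and 3.0 mg/dL; SI limits of 0.40 and 0.41 mmol/L, both of the at-or-below kind.

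**Assumptions not in the documents:** molar mass of magnesium 24.305 g/mol. For the comparison rows: calcium 40.078 g/mol, phosphorus 30.974 g/mol, and 0.357 mmol/L per mg/dL for BUN.

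**Formula:** mmol/L = (mg/dL × 10) / molar mass.

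1. *Low limit, the plan's own figure.* 1.0 × 10 / 24.305 = 0.411 mmol/L. Both printed SI entries, 0.40 and 0.41, are versions of this low limit.
2. *High limit.* 3.0 × 10 / 24.305 = 1.234 mmol/L. No SI entry corresponds to it.
3. *Check without an outside constant.* 3.0 mg/dL is three times 1.0 mg/dL. Scaling the table's own low entries gives 3 × 0.40 = 1.20 and 3 × 0.41 = 1.23 mmol/L. The missing entry therefore lies between 1.20 and 1.23 on the table's own figures.
4. *Is magnesium the exception?* The rows with two limits in standard units are BUN, sodium, chloride, potassium, calcium, phosphate, platelets, leukocytes, granulocytes, lymphocytes and red cells. All eleven have a low and a high SI limit. The chemistry pairs that need conversion agree with the printed values:
   - calcium: 7.5 × 10 / 40.078 = 1.871 (printed 1.87); 11.6 × 10 / 40.078 = 2.894 (printed 2.89)
   - phosphate: 2.0 × 10 / 30.974 = 0.646 (printed 0.65); 5.3 × 10 / 30.974 = 1.711 (printed 1.71)
   - BUN: 2 × 0.357 = 0.714 (printed 0.7); 30 × 0.357 = 10.71 (printed 10.7)
5. *The columns applied to example results:*

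| Result, mmol/L | Same result, mg/dL | mg/dL column | SI, other countries | SI, Canada |
|---|---|---|---|---|
| 0.39 | 0.95 | notable | notable | notable |
| 0.405 | 0.98 | notable | not notable | notable |
| 1.0 | 2.43 | not notable | not notable | not notable |
| 1.5 | 3.65 | notable | not notable | not notable |
| 2.5 | 6.08 | notable | not notable | not notable |

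The last two rows are the point: the same result is notable in one column and not in the other. The second row shows the country split in the low limit.

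**The case against.** The strongest reply is that the table alone does not show that anything is missed. SAP 9.2 refers to Appendix A without naming a unit column or a conversion step. A program that standardises to mg/dL would flag every high value. This stands, so the consequence is conditional on the SI column being applied as printed.

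Other outputs give partial cover. SAP 9.2 also plans by-visit statistics and shift tables by normal range, where high magnesium would be visible in either unit. Clinically significant abnormal values are reportable as adverse events (Protocol 6.5.4 and 7.1). This also stands, with one limit: Protocol 9.4.1.2 describes shift tables on clinically notable ranges, and tables built that way would share the gap.

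On alerts, Protocol 6.5.4 says that alerting values are also supplied in a laboratory manual, which is not among the documents. A missed alert is possible but cannot be inferred.

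A line lost when the PDF was read is not excluded, because the SAP table largely reproduces the protocol's. The two readings are laid out differently and agree, and neither marks a redaction, so a true omission is more likely.

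Finally, the 0.40/0.41 split is labelled by country and may be deliberate. It is close to a rounding difference: 0.40 is just under 3% below 0.411, and the BUN low limit of 0.7 is about 2% below 0.714. This stands too. The split needs an explanation, but it is not shown to be an error.

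**Conclusion.** The omission holds: in both appendices, notable magnesium has an upper limit in mg/dL and none in SI. What follows is limited. If the SI column is applied as printed to mmol/L results, values at or above 3.0 mg/dL (about 1.23 mmol/L) do not enter the SAP 9.2 notable counts and listings, and may not trigger an alert.

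A reader might infer more, and the documents do not support it:
- *High magnesium is never flagged, or a high-magnesium row will read zero.* No unit column is named, and no separate row for high magnesium is planned.
- *The SI rule points the opposite way to the 3.0 mg/dL limit.* This rests on how lines happen to align in the extracted protocol table. Both SI entries are low limits, so neither is the counterpart of 3.0 mg/dL.
- *One low limit should apply in all countries.* The documents state two, each labelled, and give no basis for choosing between them.

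The impact is minor. The safety analyses are descriptive (Protocol 9.4.1), the documents give no count of affected results, and the number is probably small. Part 2 is not affected: its SAP summarises no chemistry results. The figure of 1.23 mmol/L rests on the assumed molar mass; the table's own entries give 1.20 to 1.23.

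**What to change.** - In SAP Part I, Appendix A, and Protocol Appendix 1, reconcile the two magnesium columns. Add the SI equivalent of the sponsor's existing 3.0 mg/dL limit, about 1.23 mmol/L, and describe it as a conversion.
- In SAP Part I, 9.2, state which unit column governs the notable criteria, or that results are converted to one unit before flagging.
- Reconcile the country-specific SI low limits with the 1.0 mg/dL limit, or state the reason for the split and how it is handled in pooled summaries.
- Check whether the analysis program and the central laboratory's alert settings included a high limit for magnesium. If the program did not, rerun the notable-value outputs.

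The cost is one table cell in each document, a sentence or two in SAP 9.2, and one check each of the program and the alert settings. No new data are needed.

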Appendix B: Clinically notable Vital sign values

CRITERIA FOR NOTABLE VITAL SIGN ABNORMALITIES

NOTABLE VITAL SIGNS	
Vital Sign Variable	Notable Criteria
Pulse (beats/min)	>120bpm or Increase of ≥ 15 bpm from baseline Or < 50bpm or Decrease of ≥ 15 bpm from baseline
Systolic BP (mmHg)	≥ 160 mm Hg or Increase of ≥ 20 mm Hg from baseline Or ≤ 90 mm Hg or Decrease of ≥ 20 mm Hg from baseline
Diastolic BP (mmHg)	≥ 100 mmHg or Increase of ≥ 15 mm Hg from baseline Or ≤ 50 mmHg or Decrease of ≥ 15 mm Hg from baseline
Temperature ($^{\circ}\text{C}$)	>38.3 $^{\circ}\text{C}$ / 101 $^{\circ}\text{F}$
Body Weight (kg)	$\pm 7\%$ from baseline weight

Clinical Development

FTY720 (Fingolimod)

CFTY720D2399 / NCT01201356

A single arm, open-label, multicenter study evaluating the long-term safety and tolerability of 0.5 mg fingolimod (FTY720) administered orally once daily in patients with relapsing forms of multiple sclerosis

RAP Module 3 – Detailed Statistical Methodology for D2399 final CSR full analysis – study part 2

Author:  Trial Statistician;  Novartis
Trial Statistician

Document type: RAP Documentation

Document status: Final Version 1.0

Release date: 26NOV2018

Table of contents

	List of abbreviations	4
1	Overview.....	5
2	General strategies of data presentation.....	5
2.1	Allocated treatment	5
2.2	Precision rules	5
2.3	Time frames, baseline, and visit windows	6
2.3.1	Database lock for Study part 2.....	6
2.3.2	Study day	6
2.3.3	Baseline and post-baseline.....	6
2.3.4	Variables Summarized by Visits	7
2.4	Imputation of Incomplete Dates	8
2.5	Analysis sets.....	8
2.5.1	Subgroups	9
3	Protocol Deviations.....	10
4	Patient Disposition.....	10
5	Background and demographic characteristics	11
5.1	Core study	11
5.2	Demographics	11
5.3	MS disease history characteristics before enrollment in core study	11
5.4	MS medication history prior to enrollment in core study	12
6	Study drug.....	12
6.1	Duration of exposure.....	12
7	Concomitant medication	12
7.1	Imputation of concomitant medication start date.....	12
7.2	Imputation of concomitant medication end date.....	13
7.3	Concomitant medication analyses.....	13
8	Efficacy evaluation	14
8.1	Analysis of MS Relapses	14
8.1.1	Relapse date imputations and handling of duplicate relapse records	14
8.1.2	Annualized relapse rates	16
8.1.3	Time in study.....	17
8.1.4	MS relapses analyses.....	17
9	Safety evaluation.....	18

9.1	Adverse events	18
9.1.1	Imputation of adverse event start date.....	18
9.1.2	Adverse events analyses	19
9.1.2.1	Adverse events during the study part 2	20
9.1.2.1.1	Occurrence of adverse events	20
9.1.2.1.2	Incidence rate of adverse events	21
9.1.2.1.3	Regulatory adverse events report	21
9.1.2.2	Adverse events during the fingolimod treatment period	22
9.2	Laboratory	22
9.3	Routine vital signs.....	22
9.4	Dose monitoring administration.....	23
9.4.1	Vital signs	23
9.4.2	Electrocardiograms	23
10	Sample size and power considerations	24
	Appendices	25
	Appendix A: Clinically notable Vital sign values	25

List of abbreviations

AE	adverse event
ARR	annual relapse rate
BPM	beats per minute
eCRF	electronic case report/record form
ECG	electrocardiogram
FDD	First dose of study drug (among all studies)
FDF	First dose of fingolimod
HR	heart rate
MS	multiple sclerosis
p.o.	by mouth
SAE	serious adverse event
s.c.	subcutaneously

1 Overview

Study CFTY720D2399 is a single arm, open-label, multicenter study evaluating the long-term, safety, tolerability and efficacy of 0.5 mg fingolimod (FTY720) administered orally once daily in patients with relapsing forms of multiple sclerosis (MS). The term ‘study part 2’ is used to define the last extension phase of CFTY720D2399 study throughout this document, indicating that CFTY720D2399 is the extension of all historical fingolimod studies, and the term ‘study part 2’ means that this CFTY720D2399 study is the extension phase of CFTY720D2399 study part 1, which is completed in Jul2017. This study allows prior fingolimod study patients who are unable to obtain fingolimod outside a clinical trial to get access to the drug. These patients include a subset of patients participating in part 1, and other eligible patients from ongoing fingolimod trials (e.g., CFTY720D2312). The purpose of study part 2 is to obtain additional long-term safety and tolerability data.

The end of the study treatment visit is planned for 30 June 2018. Individual patient’s end of treatment visits should occur at their routine 6 monthly scheduled visit closest to 30 June 2018 to ensure all patients complete within the window for the end of the study.

2 General strategies of data presentation

Statistical Analysis System (SAS) version 9.3 or higher will be used to perform all analyses.

In general, variables will be summarized using frequency distributions for categorical variables and summary statistics for continuous variables. Summary statistics for continuous variables will include n, mean, standard deviation, minimum, first quartile (Q1), median, third quartile (Q3) and maximum.

Note that, the population sets are derived based on Virtual Data Warehouse, which does not include CFTY720D2312 and CFTY720D2402 studies, thus patients from the 2 studies are not included for any summary, and only information in the study part 2 (from part 2 raw data) is included for listing purposes.

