## 3 Investigational plan

### 3.1 Study design

This study uses an open-label, multi-center, single treatment arm design allowing patients participating in the fingolimod multiple sclerosis clinical development program to enroll in order to collect additional long-term safety, tolerability, efficacy, and health outcomes data.

This study has two parts:

[figure not shown]
- Part One, collecting long-term safety, tolerability, efficacy, and health outcomes data through approximately 30-Jun-2016, and
- Part Two\*, collecting limited safety data until approximately 30-Jun-2018, in a subset of patients participating in Part One, and other eligible patients from ongoing fingolimod trials (e.g., CFTY720D2312).

\*Eligibility for Part Two is defined as prior fingolimod study patients who are unable to obtain fingolimod outside a clinical trial.

By June 2016, investigators must determine commercial Gilenya eligibility for all active study patients (i.e., reimbursed for commercial Gilenya). Patients able to obtain commercial Gilenya will then have their End of Study (Part One) visit and exit the study, regardless of their post-study treatment decision (i.e., continuing on Gilenya commercially or transitioning to another treatment option). Patients discontinuing or completing the study at Part One who do not continue on commercial Gilenya must return for two follow-up study visits, 3-months and 6-months post-last dose of fingolimod. Patients who choose to continue on commercial Gilenya outside the study are exempted from the follow-up visits.

Patients not eligible for reimbursed, commercial Gilenya will be offered continued study participation in Part Two until their scheduled study visit closest to 30-Jun-2018 (+/- 30 day visit window), with a reduced assessment schedule (see Table 6-2), for the purpose of collecting additional long-term safety and tolerability data in support of the primary study objective. Patients discontinuing or completing the study after entering Part Two who do not continue on commercial Gilenya must return for one follow-up study visit, 3-months post-last dose of fingolimod. Patients who choose to continue on commercial Gilenya outside the study are exempted from the follow-up visit.

Patients enrolling in either part of the study from blinded studies will remain blinded to the identity of the treatment in the previous study. In order to maintain the blind, the monitoring

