**Table 6-2 Assessment schedule (Study Part Two)**

Visit No.*	Visit 201A 	Visit 201B 	Visit 211 	Visit 212 	Visit 202	Visit 203	Visit 204...	Study Completion or Premature DC 	FU 3 
Study month	Day1 	Day1  (First Dose Monitor)	Month 1 	Month 3 	Month +6/6	Month +12/12	Every 6 Months until SC		
Informed consent 	XS	XS							
Demography 	S1	S1							
Inclusion/exclusion criteria	XS	XS							
Previous Study	XS	XS							

Details 									
Medical History 	S1	S1							
Concomitant meds	XS	XS	XS	XS	XS	XS	XS	XS	XS
Physical/ neurological exam	S1	S1	S	S	S	S	S	S	S
Skin exam by a qualified physician 		Record in source as needed							
Eye Exam 	S1	S1		S	S				
OCT/Ophthalmic Exam				S 	S 				
PFTs		Record in source as needed							
Vital signs	S1	S1	XS	XS	XS	XS	XS	XS	XS
Hematology/ Chemistry/ Pregnancy 			S	S	S	S	S	S	S
Dispense study drug	S	S		S	S	S	S		
Collect unused study drug			S	S	S	S	S	S	
First dose monitoring 		XS	Record as needed						
First Dose ECG 		XS							
Dosage Administration Record	XS	XS		XS	XS	XS	XS	XS	
MS relapse	XS	XS	XS	XS	XS	XS	XS	XS	XS
Steroid Use	XS	XS	XS	XS	XS	XS	XS	XS	XS
Adverse events/ SAEs	XS	XS	XS	XS	XS	XS	XS	XS	XS
Study Completion								XS	

1. Visit 201A is applicable for current patients or those transitioning from another open-label fingolimod study
2. Visits 201B, 211 and 212 are applicable only for those patients transitioning from a blinded fingolimod study which has comparator treatment arms (placebo, or active comparator, e.g. study CFTY720D2312), from the comparator arm of an unblinded fingolimod study, or for patients who have interrupted treatment for durations as outlined in Appendix 4.
3. Informed consent, demography, previous study details, and medical history are only applicable if the patient enters Study Part Two from another study (i.e., not applicable for patients transitioning from Study Part One).
4. A qualified physician includes a dermatologist OR a physician who has participated in a licensed training program.
5. To be performed by the treating physician.

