### **Safety set**

The Safety set will consist of all patients that received at least one dose of study drug in this long-term follow-up study.

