## **9.4 Analysis of the primary variable(s)**

### **9.4.1 Variable**

Long-term safety will be assessed based on adverse events (AEs), laboratory and vital signs as well as other investigations performed when clinically indicated.

Analysis of the safety variables will be conducted on

[figure not shown]
- Safety set: for any analyses including data collected during the long-term follow up study only
- Fingolimod safety set: for analyses including data from first dose of fingolimod in the original core/extension study, if there is any, and in the long-term follow up study.

Given the nature of the design, the data will be presented using descriptive statistics and no inferential analyses are planned.

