2.1 Allocated treatment

All patients during the study part 2 are treated with fingolimod 0.5 mg per day, even though patients may have been assigned a different dose (5 mg, 1.25 mg) in their initial fingolimod trial. Unless otherwise specified, all summaries will only present the “fingolimod 0.5 mg” group, which indicates the dose level used during the study part 2. For adverse events by yearly interval, additional summaries will be provided by “highest fingolimod dose 0.5 mg” group, which indicates the subjects’ highest fingolimod dose throughout all fingolimod trials.

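### Part 2 SAP: D2312 and D2402 patients are left out of every Part 2 summary only because the data warehouse lacks their earlier studies, although their Part 2 data are held and listed

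*SAP*

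**What the plan says.** Part 2 SAP, section 2 (General strategies of data presentation), derives the population sets from the Virtual Data Warehouse. D2312 and D2402 are not in that warehouse, and "thus patients from the 2 studies are not included for any summary". The same sentence keeps their Part 2 raw data for listings. No other reason is given.

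Part 2 SAP 2.1 states: "All patients during the study part 2 are treated with fingolimod 0.5 mg per day". The protocol's Safety set (9.1) is "all patients that received at least one dose of study drug in this long-term follow-up study", and 9.4.1 assigns its use: "Safety set: for any analyses including data collected during the long-term follow up study only". Protocol 3.1 describes Part Two as collecting safety data "in a subset of patients participating in Part One, and other eligible patients from ongoing fingolimod trials (e.g., CFTY720D2312", and the Part 2 SAP overview repeats this.

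Part 1 SAP, section 2, has a parallel rule: core data from these two studies enter no summary, and their Part I data are for listing only.

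**The concern.** The reason for the exclusion concerns where earlier-study data are stored, not whether the patient was treated or followed in Part 2. Several Part 2 tables need nothing from the earlier studies. Additional long-term safety data are the stated purpose of Part 2, so leaving treated patients out of its safety tables bears on the primary objective.

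First-dose monitoring is the sharpest case. Protocol Table 6-2, footnote 2, reserves Visit 201B for three groups: entrants from blinded studies with comparator arms, entrants from the comparator arm of an unblinded study, and patients restarting after an interruption. D2312 is the only study named there, yet its entrants are taken out of the monitoring summaries.

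Because the Part 1 SAP also confines these patients to listings, on these plans they reach no summary table in either part.

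**Working it through.** The documents give no figure to reproduce: the study is descriptive, and the Part 2 SAP states neither a Part 2 sample size nor a count for these studies. The check is mainly text against text.

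**Definitions side by side**
- Protocol 9.1: at least one dose in this study, with no condition on earlier study or data source.
- Part 2 SAP 2.5: all who entered Part 2 with at least one fingolimod dose in any study, less deviation codes 5 and 8. The set is also called a subset of the fingolimod safety set, whose exclusions depend on core-study deviation codes. The warehouse does not hold the core data of D2312 and D2402.
- Part 2 SAP 4 and 9.1.2.1.1: D2312 and D2402 patients are described as members of the enrolled set, but are only listed.
- Part 2 SAP 2: the same patients are in no summary.

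The last line cannot be reconciled with the first three.

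**What each table needs**
- Part 2 data only: overall disposition (4); exposure from first Part 2 dose (6.1); incidence rates from first Part 2 dose (9.1.2.1.2); dose monitoring (9.4, 9.4.1); newly occurring AEs, counted from Part 2 consent (9.1.2.1.1). Table 6-2, footnote 3, makes consent "only applicable if the patient enters Study Part Two from another study", so direct entrants have that date. D2312 or D2402 patients who came through Part One can be handled like all other Part One patients.
- Onset window from first fingolimod dose in any study, applied to Part 2 records: the general AE tables (9.1.2.1) and concomitant medications (7.3). The registry tables (9.1.2.1.3) count on-treatment events in the Safety set. All of these can be run with a window from first D2399 dose.
- Prior-study data: disposition by cumulative exposure (4), demographics and history (5.2–5.4), relapse analyses (8.1.4), AEs by year since first fingolimod dose (9.1.2.2).
- Part 1 baseline: vital-sign change (2.3.3, 9.3).

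The warehouse gap justifies exclusion only from the prior-study group.

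**Patient-time per excluded patient**

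Inputs: Part Two nominally runs from 30-Jun-2016 to 30-Jun-2018 (protocol 3.1). Part 2 SAP 2.3.1 allows the last visit within 3 months of the end date. Time at risk for an event-free patient adds 45 days (9.1.2.1.2). Interruptions are ignored.

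| Entry | Exit | Days | Exposure (days/365.25) | At risk ((days+45)/365.25) |
|---|---|---|---|---|
| 30-Jun-2016 | 30-Jun-2018 | 730 | 2.00 y | 2.12 y |
| 30-Jun-2016 | 30-Sep-2018 | 730 + 92 = 822 | 2.25 y | 2.37 y |
| 31-Oct-2016 (Part 1 SAP 2.3.1) | 30-Jun-2018 | 607 | 1.66 y | 1.79 y |

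For an assumed 10, 50 or 100 excluded patients, the nominal time at risk removed is 21, 106 or 212 patient-years. With exit at the 3-month limit it is 24, 119 or 237.

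**Effect on an incidence rate**

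Let f be the excluded patients' share of Part 2 patient-time and r their event rate relative to the others. With rate λ in those included, the full rate is λ[(1−f)+fr] and the reported rate is λ. So reported/full = 1/[(1−f)+fr]. Both f and r are assumptions.

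| f | r = 0.5 | r = 1 | r = 2 |
|---|---|---|---|
| 5% | 1/0.975 = 1.03 | 1.00 | 1/1.05 = 0.95 |
| 10% | 1/0.95 = 1.05 | 1.00 | 1/1.10 = 0.91 |
| 20% | 1/0.90 = 1.11 | 1.00 | 1/1.20 = 0.83 |
| 30% | 1/0.85 = 1.18 | 1.00 | 1/1.30 = 0.77 |

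**The case against.** The best counter-argument is that Part Two has its own population rule. Protocol 9.1.1 bases every analysis that includes Part Two data on a subgroup dosed after completing Part One. Read literally, that omits patients who enter Part Two directly from D2312, so a reader who infers that the SAP breaches the protocol for every D2312 and D2402 patient goes too far. This stands in part: for direct entrants the protocol is ambiguous. But protocol 3.1 and Table 6-2 plainly provide for them, the SAP does not rely on 9.1.1, and that clause would not remove patients who came through Part One.

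The exclusion is also openly stated, the study is descriptive, and AEs, SAEs, deaths and early discontinuations of these patients are listed. All of that is correct, so the data are absent from tables, not lost.

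Three other stronger inferences fail:
- That the tables understate risk. Nothing in the documents says whether these patients have more or fewer events.
- That registry counts must be short. Those tables count patients with events and occurrences, so they are short only if the excluded patients had qualifying events.
- That the monitoring summary would be empty. Restarts and entrants from other studies could still contribute.

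Finally, including these patients in Part 2 tables creates a mismatch with the Part 1 tables. That is a real cost of the fix.

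**Conclusion.** The concern holds in this form. The Part 2 SAP removes treated patients from every Part 2 summary for a data-storage reason that does not reach the tables built on Part 2 data alone. It conflicts with the protocol's Safety set, clearly for those who came through Part One and arguably for direct entrants, and it conflicts with the SAP's own set definitions.

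The consequence is incomplete Part 2 safety tables: patients, patient-years and any events they had. The size cannot be determined. The patient-year figures are nominal and not upper bounds, since entry and exit dates vary around the planned ones. The rate ratios rest wholly on assumed values of f and r; at equal event rates there is no bias in the rate, only smaller counts and denominators. D2312 is a named Part Two source, but no document says how many D2312 or D2402 patients entered.

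This should be fixed before database lock. It is not grounds for saying that safety data are lost or that rates are biased in a known direction.

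**What to change.** Amend the Part 2 SAP:

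1. Build the Part 2 enrolled, safety and follow-up sets from the Part 2 database. Delete the blanket exclusion in section 2 and the subset condition on the Safety set in 2.5.
2. Include D2312 and D2402 patients in overall disposition (4), exposure (6.1), newly occurring AEs (9.1.2.1.1), incidence rates (9.1.2.1.2) and dose monitoring (9.4, 9.4.1). In the general AE tables (9.1.2.1), registry tables (9.1.2.1.3) and concomitant medications (7.3), use a footnoted window from their first D2399 dose.
3. Keep the exclusion, with the number excluded in a footnote, for analyses that need prior-study data: disposition by cumulative exposure (4), 5.2–5.4, 8.1.4 and 9.1.2.2. For vital-sign change and change-based notable criteria (2.3.3, 9.3), exclude only patients without a Part 1 baseline. Those who came through Part One keep theirs. Direct entrants at Visit 201A have no first-dose monitoring readings to serve as a baseline, and Table 6-2 keeps Day 1 routine vital signs in source documents only.
4. State that the Part Two subgroup is taken as at least one dose in Part Two, and record that this differs from the wording of protocol 9.1.1.

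The cost is one SAP amendment before the lock planned for December 2018/January 2019 and extra programming on raw data already used for listings; no new data are collected. Denominators will differ between Part 2-only and cumulative tables, and between Part 1 and Part 2 tables because of the Part 1 rule. Some tables will carry two onset windows.

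If the exclusion is kept, the SAP should declare it as a departure and the report should give the patients, patient-years, AEs, SAEs and deaths excluded.
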